### 3.7. Biomarker Assessments

A key objective of the biomarker analyses that will be performed in this study is to investigate biomarkers that are potentially predictive of treatment benefit with the combination of avelumab and SOC CRT. In addition, biomarker studies of tumor and blood biospecimens will be carried out to help further understand the mechanism of action, as well as potential mechanisms of resistance, to the combination of avelumab with SOC CRT. Tumor and blood biospecimens as required for the various analyses will be collected as described in the [Schedule of Activities](#) table.

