**Table 1. Summary of Major Changes in SAP Amendments**

Version	Version Date	Summary of Changes
3	30-Aug-2019	
Updated the target number of events for PFS and OS and associated operating characteristics as per protocol amendment 3 in Section 2 “Introduction”, Section 5.1 “Hypothesis and Decision Rules” and subsections and Section 7.2.2 “Interim analysis for OS”.
 
CCI
 
Section 3.4.1 “Study drug, study treatment and baseline definitions” – the definition of start dates of study treatment within each treatment phase was added to support the summaries of safety by treatment phase.
 
Section 6.2.2.2 “Sensitivity analyses for progression-free survival” – per FDA request, sensitivity analyses of PFS by Blinded Independent Central Review (BICR) per standard RECIST v1.1 were added; early discrepancy rate and late discrepancy rate interpretations were corrected.
 
Section 6.2.2.4 “Locoregional failure” – included an additional possible censoring reason associated with Distant Metastatic failure in Table 17 “Time to LRF Censoring Reasons and Hierarchy”.
 
Section 6.2.2.5 “Distant metastatic failure” – included an additional possible censoring reason associated with Locoregional failure in Table 19 “Time to DM Censoring Reasons and Hierarchy”.
 
Section 6.2.2.6 “Neck dissection” – the positive and negative predictive values definitions were corrected to refer to individual lesions rather than to patients as patients may have multiple lesions.
 
Section 6.2.2.7 “Pathologic complete response” – pathologic complete responder definition was clarified for patients with more than one resected lesion.
 
Section 6.2.6 “Biomarker endpoints” – biomarker analysis was simplified to focus on the analyses associated with the pre-specified objectives.
 
Section 6.2.7.3 “Analysis of PK and safety by immunogenicity status” – clarified that the analysis of IRRs by ADA status will be conducted for IRRs associated with avelumab.
 
Section 6.5.1.3 “Disease characteristics” - “Time since diagnosis of local/regional recurrence of disease” – deleted as data not collected in the CRF. The smoking history analysis was simplified.
 
Section 6.5.2.1 “Patient disposition” – summaries for CRT Phase were added; frequency of patients completing each study phase was added; frequency of patients entering CRT Phase and frequency of patients entering Maintenance Phase were added.
 
Section 6.5.3.1 “Exposure to avelumab or matching placebo” – duration of exposure to avelumab was changed from days to weeks; duration of exposure and total number of infusions to avelumab across all phases was added.
 
Section 6.5.3.2 “Exposure to cisplatin” – considerations regarding split dose were added.
 
Section 6.5.3.3 “Exposure to IMRT” – analysis of compliance was added.
 
Section 6.6.1 “Adverse events” – by treatment phase summaries of TEAEs, Serious TEAEs, TEAEs leading to death, Deaths, irAEs, and IRRs were added;

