#### Secondary Objectives

- To compare the overall survival (OS) of avelumab in combination with SOC CRT vs SOC CRT alone;
- To evaluate the anti-tumor activity of avelumab in combination with SOC CRT and SOC CRT alone;
- To evaluate the overall safety and tolerability profile of avelumab in combination with SOC CRT and SOC CRT alone;
- To evaluate the PK of avelumab;

- To evaluate the PK of cisplatin (total and free);
- To assess avelumab ADAs;
- To evaluate the effect of avelumab in combination with SOC CRT and SOC CRT alone on patient-reported outcomes (PROs) of disease-related symptoms and health related quality of life (HRQoL);
- To evaluate candidate immune-related predictive biomarkers of sensitivity or insensitivity to treatment with avelumab in combination with SOC CRT in pretreatment tumor samples (eg, PD-L1 expression);
- To evaluate candidate immune-related predictive biomarkers of sensitivity or insensitivity to treatment with avelumab in combination with SOC CRT in tumor samples (eg, PD-L1 expression) after one dose of avelumab in patients who provide this optional biopsy.

CCI

[figure not shown]

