**Table 9. Outcome and Event Dates for PFS Analyses**

Scenario	Date of event/censoring	Outcome
No adequate baseline assessment and no PD and no death	Date of randomization	Censored
No adequate post-baseline tumor assessment or clinical evaluation and no death	Date of randomization	Censored
PD or death	Date of PD or death	Event
No PD and no death	Date of last adequate tumor assessment or clinical evaluation documenting no PD	Censored

The primary efficacy analysis will compare the PFS time between Arm A and Arm B, and will be performed using a 1-sided stratified log-rank test as described in Section 5.1.

The treatment effect will be estimated using a Cox's Proportional Hazard model stratified by the randomization strata to calculate the hazard ratio. Each stratum will define a separate baseline hazard function (using the 'STRATA' statement in SAS PROC PHREG), ie for the i-th stratum the hazard function is expressed as:  $h(i;t) = h(i,0;t) \exp(x\beta)$ , where  $h(i,0;t)$  defines the baseline hazard function for the i-th stratum and  $x$  defines the treatment arm (0=Arm B, 1= Arm A) and  $\beta$  is the unknown regression parameter.

Ties will be handled by replacing the proportional hazards model by the discrete logistic model (Ties=Discrete option in SAS PROC PHREG).

In order to account for the group sequential design in this study, the repeated CI (RCI) method (Jennison and Turnbull, 2000^11), will be used to construct the 2-sided RCIs for the hazard ratio at the interim and the final analyses of PFS.

In addition, the unadjusted 95% CIs for the hazard ratio will also be reported at the interim and the final analyses for PFS.

Kaplan-Meier estimates (product-limit estimates) will be presented by treatment arm together with a summary of associated statistics including the median PFS time with 2-sided 95% CIs. In particular, the PFS rates at 12, 24, 36, 48 and 60 months will be estimated with corresponding 2-sided 95% CIs. The CIs for the median will be calculated according to Brookmeyer and Crowley (1982) and the CIs for the survival function estimates at the time points defined above will be derived using the log-log transformation according to Kalbfleisch and Prentice (2002) (conftype=loglog default option in SAS Proc LIFETEST) with back transformation to a CI on the untransformed scale. The estimate of the standard error will be computed using Greenwood's formula.

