#### **6.2.6. Biomarker endpoints**

There are two sets of biomarkers, those collected at screening (pre-treatment tumor sample), and the optional tumor sample after one dose of avelumab. The optional tumor samples will be analyzed separately.

Summary statistics for pre-treatment biomarkers will be presented by treatment arm and overall. Summary statistics for on-treatment biomarkers will additionally include the ratio to baseline for continuous biomarkers, and a contingency table for non-continuous biomarkers, as appropriate.

Continuous biomarkers will be split at the median ( $<$  and  $\geq$  median), and will be included as a covariate in an exploratory Kaplan-Meier analysis for PFS, as described in Section 6.1.1.1; no other covariates will be included. Non-continuous biomarkers will either be split at an appropriate point in their distribution, and classified as above and below the split (0,1), or the actual categories will be included in the survival analysis.

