### 6.4. Subset Analyses

Subset analyses will be performed for PFS, OS, uOR and DR based on the FAS for the subgroups defined below.

The following subgroups will be defined and used for analyses:

- Randomization stratification factors
  - Tumor (T) stage (<T4 vs T4; T4=Reference);
  - Nodal (N) stage (N0/N1/N2a/N2b vs N2c/N3; N2c/N3=Reference);
  - HPV status (positive vs negative; negative=Reference) as measured by p16 expression by IHC.

- Age
  - Age < 65 years (Reference);
  - Age ≥ 65 years.
- Gender
  - Male (Reference);
  - Female.
- Race
  - White (Reference);
  - Asian;
  - Black or African American;
  - Other.
- Ethnicity
  - Hispanic or Latino;
  - Not Hispanic or Latino (Reference).
- Pooled Geographical Region
  - North America;
  - Western Europe (Reference);
  - Eastern Europe;
  - Asia;
  - Rest of the World (Australasia, Latin America, Africa and/or Middle East will be included as additional subgroups if including > 10% of the overall randomized population).
- ECOG Performance Status at Baseline
  - 0 (Reference);
  - 1.
- Subsite of Primary Diagnosis
  - Oral cavity (Reference);
  - Oropharynx;
  - Larynx;
  - Hypopharynx;
  - Other.

Subset analyses for PFS, OS and DR will use the primary censoring rules described in Sections 6.1.1.1 and 6.2.2.1. All the subgroup analyses are exploratory. Treatment arms will be compared for PFS and OS using a 2-sided unstratified log-rank test for each subgroup

level and the unstratified HR and its corresponding 95% CI will be computed per subgroup level.

All the subgroup analyses will be exploratory; no adjustment for multiplicity will be performed. In the case of a low number of patients within a category (<5% of the randomized population), the categories will be pooled.

To assess the heterogeneity of treatment effects for PFS and OS across the subgroup levels, two Cox regression model will be fitted with PFS or OS, respectively, as the dependent variable and subgroup, treatment, and with and without the treatment-by-subgroup interaction as explanatory variables.

- Model 1: factors + treatment + subgroup
- Model 2: factors + treatment + subgroup + treatment×subgroup-variable

A p-value for the interaction test (Wald's test) will be provided together with the HR and corresponding 95% CI for the interaction model parameter.

The HR for PFS and OS and corresponding 95% CIs for all subgroups will also be presented in a forest plot.

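### SAP 6.2.6 plans no treatment-by-marker estimate for pre-treatment PD-L1 or CD8 in the legible text, although the objective is predictive biomarkers

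*SAP*

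**What the plan says.** A secondary objective in SAP 2.1 is "To evaluate candidate immune-related predictive biomarkers of sensitivity or insensitivity to treatment with avelumab" plus CRT in pre-treatment tumor samples, with PD-L1 as the example. Protocol 3.7 calls it a key objective to "investigate biomarkers that are potentially predictive of treatment benefit with the combination of avelumab and SOC CRT". PD-L1 expression and tumor-infiltrating CD8+ lymphocytes are the named biomarker endpoints (SAP 3.2.6, Table 4).

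SAP 6.2.6 plans descriptive marker summaries and one analysis against outcome. A continuous marker is first dichotomized at its median; the section then says that it "will be included as a covariate in an exploratory Kaplan-Meier analysis for PFS, as described in Section 6.1.1.1; no other covariates will be included". For the rest, "Non-continuous biomarkers will either be split at an appropriate point in their distribution", or the actual categories are used. The version log says of this section that "biomarker analysis was simplified to focus on the analyses associated with the pre-specified objectives".

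The cross-referenced Section 6.1.1.1 contains a stratified log-rank test, a stratified Cox treatment hazard ratio, and then: "Kaplan-Meier estimates (product-limit estimates) will be presented by treatment arm together with a summary of associated statistics including the median PFS time".

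SAP 6.4 gives an unstratified treatment hazard ratio per subgroup level. It also fits a model with a treatment-by-subgroup term, for which an interaction p-value "will be provided together with the HR and corresponding 95% CI for the interaction model parameter". Its subgroups are T stage, N stage, HPV status, age, gender, race, ethnicity, region, ECOG status and primary subsite.

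**The concern.** A marker is predictive when the treatment effect differs across its levels. The quantity that addresses this is a contrast of treatment effects between levels, with its uncertainty. By-arm curves, medians and landmark rates within each level describe the pattern but give no estimate or interval for that contrast. Readers would then compare curves by eye, which invites over-reading in groups of this size.

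The SAP estimates effect modification for gender and region but, as far as can be read, not for the two markers named for its own objective. The data would support the estimate: baseline tissue is mandatory (Protocol 6.2.1.1) and the control arm is randomized.

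This point covers pre-treatment samples only. The analysis set for the optional on-treatment biopsy (SAP 4.3.3) requires a dose of avelumab and so has no control arm.

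**Working it through.** **What each reading of 6.2.6 would deliver.** Kaplan-Meier estimation takes no covariates, so the sentence needs interpreting.

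| Reading | Treatment HR per marker level | Treatment-by-marker estimate |
|---|---|---|
| Kaplan-Meier curves by arm within marker level | no | no |
| Cox model with a marker term and no interaction | no | no |
| All of 6.1.1.1, including its Cox model, repeated within each level | yes | no |

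The right-hand column is the same throughout, so that part of the finding does not depend on the reading. The middle column does.

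**Whether another legible section fills the gap.** The list in SAP 6.4 omits PD-L1 and CD8. The multivariable Cox analysis in SAP 6.2.2.2 points to the same subgroups and rules out interactions. No legible protocol text adds such an analysis.

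**Design figure.** Protocol 9.1 gives 289 PFS events for at least 90% power at a hazard ratio of 0.68, 1-sided 0.025, with 1:1 allocation.
- Fixed design (Schoenfeld): 4 × (1.960 + 1.282)² / (ln 0.68)² = 283 events.
- Fixed-design power at 289 events: 0.906.
- Two looks at 217 and 289 events with Lan-DeMets O'Brien-Fleming spending: interim alpha 0.0097, z = 2.338, final nominal p = 0.0221, power 0.902.

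The plan's figures reproduce.

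**Precision of the missing estimates.** Let d1 and d2 be the events in the two marker levels. I assume events split equally between arms and in proportion to marker availability and split. The documents do not state how many patients will have a usable marker result, so the 80% rows are an assumption.
- SE of the log HR in one level = 2/√d.
- SE of the log ratio of HRs = √(4/d1 + 4/d2).
- 95% interval factor = exp(1.96 × SE).
- Ratio detectable with 80% power, 2-sided 0.05 = exp(2.80 × SE).

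For complete data and an even split, d1 = d2 = 289/2 = 144.5.
- Per level: SE = 2/√144.5 = 0.166, factor 1.39. An HR of 0.68 has an interval of 0.49 to 0.94.
- Interaction: SE = √(8/144.5) = 0.235, factor 1.59, detectable ratio 1.93.
- Power for a true ratio of 0.7: Φ(0.357/0.235 − 1.96) = 0.33.

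| Marker data | Split | d1, d2 | Per-level factors | Interaction SE | Interaction factor | Detectable ratio |
|---|---|---|---|---|---|---|
| complete | 50/50 | 144.5, 144.5 | 1.39 | 0.235 | 1.59 | 1.93 (0.52) |
| 80% | 50/50 | 115.6, 115.6 | 1.44 | 0.263 | 1.67 | 2.09 (0.48) |
| complete | 25/75 | 72.2, 216.8 | 1.59, 1.31 | 0.272 | 1.70 | 2.14 (0.47) |
| 80% | 25/75 | 57.8, 173.4 | 1.67, 1.35 | 0.304 | 1.81 | 2.34 (0.43) |

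**The case against.** **The cross-reference may already import the treatment hazard ratio.** Section 6.1.1.1 is more than Kaplan-Meier, and 6.2.6 speaks of a covariate, a (0,1) coding and a survival analysis. This stands. A reader might infer that the plan excludes a treatment hazard ratio per marker level. The text supports only that it is unclear whether one is planned.

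**Redaction.** SAP 6.3, text after SAP Table 4 and protocol text after 9.3.2.11 are blacked out and may hold further biomarker analyses. This also stands, so absence from the whole plan cannot be claimed. Against it, 6.2.6 is the section for this secondary endpoint, and the version log ties its current content to the pre-specified objectives.

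**The cut-points.** A reader might infer that marker cuts are open in general. They are not. Continuous markers take the median, and both CD8 measures in Table 4 (cells per unit area and percent of cells) are continuous. What is open is any non-continuous marker, and whether PD-L1 is one, because Table 4 does not give its scale.

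**The model in 6.4 is not ready to reuse.** Model 2 includes a term called factors that the section never defines, and "Subset analyses will be performed for PFS, OS, uOR and DR based on the FAS", whereas the marker analysis needs the biomarker set. Both facts stand and shape the fix.

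**It is exploratory and imprecise.** No alpha or claim depends on it, and power for a ratio of 0.7 is 33% at best. This argues against presenting a test as decisive. It does not argue against reporting the interval, which shows the imprecision that curves alone conceal.

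**Conclusion.** The point holds in limited form. In the legible text, no treatment-by-marker estimate is planned for pre-treatment PD-L1 or CD8, although the objective is predictive biomarkers. That is so under each of the three readings of 6.2.6 set out above. Whether a treatment hazard ratio per level is planned cannot be settled from the wording.

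The benefit of correcting this is modest. Under the stated event assumptions the interaction interval factor is 1.59 at best and 1.81 with 80% availability and a 25/75 split. This is a low-cost improvement to an exploratory analysis that the sponsor should make before unblinding. It does not affect the primary result.

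**What to change.** Amend SAP 6.2.6, for PFS in the tumor-tissue biomarker analysis set (SAP 4.3.3) and for pre-treatment PD-L1 and CD8:

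1. Present Kaplan-Meier curves by treatment arm within each marker level.
2. Report an unstratified treatment hazard ratio with 95% CI per level, matching the per-subgroup hazard ratios in 6.4.
3. Fit a Cox model with treatment, marker and treatment-by-marker terms, and report the interaction hazard ratio with 95% CI. Name the adjustment set explicitly, for example none or the three randomization factors, and do not refer to Model 2 of 6.4 for it.
4. Change the sentence that bars other covariates so that it agrees with item 3.
5. State whether PD-L1 is analyzed as continuous or categorical, and fix any cut other than the median before unblinding.

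Label the analysis exploratory and aimed at estimation. The cost is SAP wording and a few extra tables with wide intervals. It needs no new data and no alpha, and leaves the primary analysis unchanged.

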### 6.2.7. Endpoints for immunogenicity data of avelumab

All analyses described below are performed for the treatment arm containing avelumab (Arm A) unless otherwise specified.

Blood samples for avelumab immunogenicity testing will be collected at pre-dose on Day 1 of the Lead-in Phase, and Days 8, and 25 of the CRT Phase. All samples should be drawn within 2 hours before the start of avelumab or placebo infusion.

Samples positive for ADA will be analyzed for titer and may be analyzed for nAb.

Patients will be characterized into different ADA categories based on the criteria defined in Table 22.

**Table 22. Patients Characterized Based on Anti-Drug Antibody Results (ADA Status)**

Category	Definition	Patients at Risk (Denominator for Incidence)
ADA never-positive	No positive ADA results at any time point; ADA-negative patients (titer < cutpoint)	Number of patients with at least one valid ADA result at any time point
ADA ever-positive	At least one positive ADA result at any time point; ADA-positive patients (titer ≥ cutpoint)	Number of patients with at least one valid ADA result at any time point
Baseline ADA positive	A positive ADA result at baseline	Number of patients with valid baseline ADA result
Treatment-boosted ADA	A positive ADA result at baseline and the titer ≥ 8×baseline titer at least once after treatment with avelumab	Number of patients with valid baseline ADA results and at least one valid post-baseline ADA result
Treatment-induced ADA	Patient is ADA-negative at baseline and has at least one positive post-baseline ADA result; or if patient does not have a baseline sample, the patient has at least one positive post-baseline ADA result	Number of patients with at least one valid post-baseline ADA result and without positive baseline ADA result (including missing, NR)
Transient ADA response	If patients with treatment-induced ADA have (a single positive ADA result or duration between first and last positive result <16 weeks) and ADA result at the last assessment is not positive.	Number of patients with at least one valid post-baseline ADA result and without positive baseline ADA result (including missing, NR)
Persistent ADA response	If patients with treatment-induced ADA have duration between first and last positive ADA result ≥16 weeks or a positive ADA result at the last assessment	Number of patients with at least one valid post-baseline ADA result and without positive baseline ADA result (including missing, NR)

ADA: anti-drug antibody, NR = not reportable.

Patients will be characterized into different nAb categories based on the criteria in Table 23. For nAb, treatment-boosted is not applicable since no titer result is available.

**Table 23. Patients Characterized Based on Neutralizing Antibody Results (nAb Status)**

Category	Definition	Patients at Risk (Denominator for Incidence)
nAb never-positive	No positive nAb results at any time point	Number of patients with at least one valid ADA result at any time point
nAb ever-positive	At least one positive nAb result at any time point	Number of patients with at least one valid ADA result at any time point
Baseline nAb positive	A positive nAb result at baseline	Number of patients with valid baseline ADA result
Treatment-induced nAb	Patient is not nAb positive at baseline and has at least one positive post-baseline nAb result; or if patient does not have a baseline sample, the patient has at least one positive post-baseline ADA result	Number of patients with at least one valid post-baseline ADA result and without positive baseline nAb result (including missing, NR)
Transient nAb response	If patients with treatment-induced nAb have (a single positive nAb result or duration between first and last positive result <16 weeks) and nAb result at the last assessment is not positive.	Number of patients with at least one ADA valid post-baseline result and without positive baseline nAb result (including missing, NR)
Persistent nAb response	If patients with treatment-induced nAb have duration between first and last positive nAb result $\geq 16$ weeks or a positive nAb result at the last assessment	Number of patients with at least one valid post-baseline ADA result and without positive baseline nAb result (including missing, NR)

ADA = antidrug antibody, nAb = neutralizing antibody, NR = no result.

The number and percentage of patients in each ADA and nAb category will be summarized.

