20. **Anti-Avelumab ADAs and Nab:** One blood sample (3.5 mL) for anti-avelumab antibodies will be collected at on Day 1 of Cycles 1 and 2 of the Maintenance Phase. All samples should be drawn within 2 hours before the start of avelumab or placebo infusion. Thereafter a pre-dose sample will be taken every 3 cycles (eg, Cycles 5, 8, 11) while a patient remains on treatment. A single sample will be taken at both EOT and 30 days post-EOT. All samples that are positive for ADA may also undergo characterization for Nab.

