### **7.4. Immunogenicity Assessments**

The sample analysis will follow a tiered approach of screening, confirmation, and titer determination. Samples tested positive for ADA may be further analyzed for neutralizing antibodies (nAb).

- Details regarding the collection, processing, storage and shipping of the blood samples will be provided to the investigator site prior to initiation of the trial in the Study Manual.
- Samples will be analyzed using a validated analytical method in compliance with Pfizer standard operating procedures.
- The samples must be processed and shipped as indicated to maintain sample integrity. Any deviations from the processing steps (eg, sample collection and processing steps, interim storage or shipping conditions), including any actions taken, must be documented and reported to the sponsor. On a case by case basis, the sponsor may make a determination as to whether sample integrity has been compromised. Any deviation from the specified sample handling procedure resulted in compromised sample integrity, will be considered a protocol deviation.
- As part of understanding the immunogenicity of the study drug, samples may be used for further characterization and/or evaluation of the bioanalytical method. These data will be used for internal exploratory purposes and will not be included in the clinical report. Samples collected for this purpose will be retained in accordance with local regulations and, if not used within this timeframe, will be destroyed.

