## nAb

- nAb ever-positive versus nAb never-positive;
- nAb: treatment-induced nAb versus nAb never-positive or baseline nAb positive.

Data listings will include immunogenicity data together with relevant PK, safety and efficacy data.

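### SAP Table 23 counts ADA-positive patients with no neutralizing-antibody result as nAb never-positive, so the nAb incidence is only a lower bound if any go untested

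*SAP*

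**What the plan says.** **Testing is permissive.** SAP 6.2.7 treats the two assays differently in one sentence: "Samples positive for ADA will be analyzed for titer and may be analyzed for nAb". The protocol agrees. Footnote 24 of Table 2, footnote 20 of Table 3 and Section 7.4.1 all state: "All samples that are positive for ADA may also undergo characterization for Nab". Section 7.4 lists screening, confirmation and titer as the assay tiers and then adds nAb analysis as something that may follow. Neither document requires an nAb assay on every ADA-positive sample.

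**Classification does not depend on testing.** In SAP Table 23, nAb never-positive is "No positive nAb results at any time point" and nAb ever-positive is "At least one positive nAb result at any time point". Both rows use the same denominator: "Number of patients with at least one valid ADA result at any time point".

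**The categories are reported and reused.** Below Table 23 the SAP states: "The number and percentage of patients in each ADA and nAb category will be summarized". Protocol 9.3.2.11 also commits to summarizing the percentage with neutralizing antibodies. SAP 6.2.7.3 then contrasts PK and safety by "nAb ever-positive versus nAb never-positive". A second contrast there sets treatment-induced nAb against a group that again includes the never-positive patients.

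**The concern.** An ADA-negative patient can reasonably be called free of neutralizing antibody without a further test, because the nAb assay is applied only to ADA-positive samples. An ADA-positive patient cannot. Table 23 puts both in the same row whenever the nAb assay was not run or gave no reportable result.

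Three things are at stake. Neutralizing antibody is a named secondary immunogenicity endpoint, and its reported incidence could be too low by an amount that the table does not reveal. The reference group in the nAb comparisons could include patients who do have neutralizing antibody. And a reader of the table could not tell an assay-negative patient from an untested one.

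**Working it through.** The documents give no nAb incidence, so there is no stated figure to reproduce. The check has two parts: the logic of the table, and an illustration of size.

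**Logic**

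1. An ADA-positive patient has a valid ADA result, and so is in the Table 23 denominator.
2. If none of that patient's samples is run in the nAb assay, which the wording allows, the patient has no positive nAb result.
3. The patient therefore meets the never-positive definition. Never-positive and ever-positive are exact complements, so there is nowhere else to go.
4. Limiting case: if no sample were nAb-tested, the table would show 0% ever-positive and 100% never-positive.

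Table 22 does not have this problem, because its never-positive definition and its denominator both rest on ADA results. In Table 23 the definition rests on nAb results and the denominator on ADA results.

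The treatment-induced nAb row of Table 23 has a related flaw. With no baseline sample, it is met by a positive post-baseline ADA result alone. An untested ADA-positive patient without a baseline sample would be both never-positive and treatment-induced.

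**Size (illustration)**

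From the documents: about 640 patients randomized 1:1, so about 320 in Arm A. Assumed, not in the documents: all 320 have a valid ADA result; ADA-positive share a = 15%; share of these truly nAb-positive q = 50%; share u of ADA-positive patients untested, with testing all-or-none per patient and unrelated to nAb status.

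- ADA-positive: 320 × 0.15 = 48. Truly nAb-positive: 48 × 0.50 = 24, or 24/320 = 7.5%.
- Reported incidence = a × q × (1 − u), that is, (1 − u) times the full-testing value.

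| | u = 0 | u = 25% | u = 50% |
|---|---|---|---|
| Untested ADA-positive | 0 | 12 | 24 |
| Reported ever-positive | 24 (7.5%) | 18 (5.6%) | 12 (3.8%) |
| Labelled never-positive | 296 | 302 | 308 |
| True positives among these | 0 | 6 (2.0%) | 12 (3.9%) |
| Untested dropped from denominator | 24/320 = 7.5% | 18/308 = 5.84% | 12/296 = 4.05% |
| Bounds, untested all negative to all positive | 7.5% | 18/320 to 30/320 = 5.6% to 9.4% | 12/320 to 36/320 = 3.8% to 11.3% |

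Dropping untested patients from the denominator recovers only about a tenth of the shortfall. At u = 50% it moves 3.75% to 4.05% against a true 7.5%. The reason is that it removes only ADA-positive patients, the ones who can be nAb-positive, and keeps every ADA-negative one. The bounds do contain the true 7.5%.

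Other assumptions change the scale but not the factor (1 − u). For ADA-positive shares of 5% to 20% and nAb shares of 25% to 50%, full-testing incidence runs from 0.05 × 0.25 = 1.25% to 0.20 × 0.50 = 10%.

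**The case against.** **The problem may never arise.** Nothing says that any ADA-positive sample will be left untested, and nAb is a named secondary endpoint with a promised summary. If every ADA-positive sample yields a valid nAb result, Table 23 is correct as it stands. This objection stands: the defect is conditional.

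**The label is literal.** Table 22 equates ADA never-positive with ADA-negative, while Table 23 says only that no positive result was seen. A reader might infer that the plan declares untested patients nAb-negative; it does not use that term. The percentages and comparisons still treat never-positive as the complement of ever-positive, so the practical effect is the same.

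**General rules might cover it.** SAP 5.2.3 shows missing observations as a separate category, and SAP 5.3.1 rules out imputation. Both yield where the SAP specifies otherwise, and Table 23 sets its own definitions and denominators. If the general rules are meant to govern here, the SAP should say so.

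**The follow-on analyses are qualified.** The repeat of the PK and safety analyses for nAb is planned only as data permit. The category counts and percentages carry no such qualifier.

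**The illustration is assumed and simplified.** Patients give repeated samples, and one positive tested sample makes a patient ever-positive, so untested samples do not translate one for one into missed patients. If high-titer samples were tested preferentially, the factor (1 − u) would not hold, and a comparison by nAb status could be exaggerated rather than diluted. This also stands.

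**Conclusion.** The point holds as a conditional defect in a classification rule. The documents permit ADA-positive patients without an nAb result, and Table 23 counts any such patient as never-positive. The reported nAb incidence is then a lower bound on what full testing would show. In the illustration it is 5.6% or 3.8% against 7.5%, for 25% or 50% of ADA-positive patients untested. Those figures rest on assumed ADA and nAb rates and on testing being unrelated to nAb status.

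Two stronger readings are not supported. A reader might infer that the nAb incidence will be understated; the documents give no basis for saying how many samples, if any, will go untested. A reader might also infer that the comparisons by nAb status are seriously compromised; even in the illustration only 2.0% to 3.9% of the reference group is misplaced, and the direction of any distortion depends on which samples are tested.

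The matter is confined to descriptive Arm A immunogenicity summaries. PFS and OS are unaffected. It is still worth correcting, because it is a stated rule that can misclassify patients on a secondary endpoint and the correction is cheap.

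**What to change.** In SAP Table 23:

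- Define nAb never-positive as ADA never-positive, or ADA-positive with valid nAb results for all ADA-positive samples and none positive.
- Class other ADA-positive patients without a positive nAb result as nAb not evaluable, in a separate row.
- Exclude the not-evaluable patients from the nAb ever-positive versus never-positive comparisons in 6.2.7.3.
- Keep the incidence denominator at patients with a valid ADA result, since removing the untested does not cure the understatement.
- Report how many ADA-positive patients were nAb-tested, and give incidence bounds with not-evaluable patients counted first as all negative and then as all positive.
- While the table is open, base the no-baseline-sample clause of the treatment-induced nAb row on an nAb result rather than an ADA result.

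The cost is SAP wording, one more table row and a slightly smaller comparison group. In the illustration the never-positive group falls from 302 to 302 − 12 = 290 at u = 25%, and from 308 to 308 − 24 = 284 at u = 50%.

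The alternative is to make nAb testing of all ADA-positive samples mandatory. The wording would then have to change consistently in SAP 6.2.7, protocol Sections 7.4 and 7.4.1, footnote 24 of protocol Table 2 and footnote 20 of protocol Table 3. That is a protocol amendment with added assay work. Non-reportable results would still need the not-evaluable row.
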